3.2 Data Analysis plan

The primary outcome measures in this study, towards being able to model electrical stimulation of the pudendal nerve will be evoked bladder contractions of at least 20 centimeters of water (cmH₂O) during the stage-4 test in at least 50% of participants. A second outcome measure will be identification of ULPP with and without stimulation. Results of the patient surveys (demographics, pelvic organ function surveys as defined above) and voiding diaries will be compared to our ability to selectively model and stimulate the pudendal nerve and cause bladder excitation and ULPP measures with stimulation to determine if there are any trends or relationships to participant characteristics.

3.2.1 Selectivity Index

For a given stimulation electrode location during the visit 2 stage-1 electrophysiology, a Selectivity Index (SI) will be calculated for each catheter or electromyogram sensor recording from distal pudendal nerve branches. This includes sensors in the proximal urethra (proximal perineal branch - PPB), distal urethra (distal perineal branch - DPB), and anal EMG (ischeal rectal nerve - IRN).

$$SI_{nerve\ X} = \frac{X}{PPB + DPB + IRN}$$

For the model-based or theoretical SI, PPB, DPB, and IRN represent the percentage of model axons activated within the proximal perineal, distal perineal, and inferior rectal nerves, respectively. For experimental SI, PPB and DPB are the maximal intraurethral pressures measured at proximal and distal sphincter locations. IRN is the maximum, normalized rectal nerve response. This SI will be used to determine whether any stimulation electrode combinations have selective recruitment of any individual pudendal nerve branches (SI > 0.67, for example). The SI calculation may be modified in some patients, as necessary, for factors such as the presence of a short urethra that only allows for a single intraurethral pressure measure (female urethras < male urethras) and/or the placement of EMG in the perineal floor between yields one or more additional sensors. During visit 4 experimental cystometrogram testing, experimental Selectivity Indexes will also be calculated as described above.

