neurostimulator lead at the pudendal nerve, as part of their normal clinical care. This is the first stage of a full implant system, in which the stimulation lead is inserted and connected to an external stimulator. If a patient responds positively to this stage-1 implant, then a following stage-2 surgery will be performed as part of their normal clinical care to implant the pulse generator (described below). These surgical procedures are typically done at the main University of Michigan hospital but may be performed at another UMHS facility as scheduling requires. [name] regularly performs these procedures as part of her clinical practice. Prior to the stage-1 and stage-2 surgeries, pre-menopausal women will undergo a urine pregnancy test. This is part of their normal clinical care as pregnancy is also an exclusion for clinical care. Once the patient is prepared for surgery, the clinical team will place up to 3 standard clinical catheters in the urethra, positioned with the pressure-sensing ports in the distal urethra, proximal urethra, and/or bladder (See Figure 3). The primary catheter will be a standard clinical-use Covidien Manoscan manometry catheter, to provide high-resolution urethra pressure data, as has been done previously [50], [51]. Other catheters will only be used to infuse some fluid into the bladder (2 catheters in total) or if the manometry catheter is unavailable (up to 3 catheters in total). A standard clinical abdominal catheter may also be placed in the rectum. The standard external anal sphincter electromyogram needles will be placed on either side of the anus for normal clinical monitoring. A pair of standard clinical electromyogram needles may also be placed in the perineal region. These catheters and electromyogram sensors will be recorded from continuously during the implant procedure. The sensors cannot transmit energy to the patient. During the surgical placement of the neurostimulator lead, if a location is identified that may be the final position then a pre-planned, structured set of stimulation parameters will be applied through each lead contact. We will vary the amplitude and pulse width of the applied stimulation pulses through the stimulation lead, staying within the programmed capabilities of the medical device. The total duration of these structured stimulation tests will last for up to fifteen minutes. This time duration is within the normal variance of the surgical procedure itself, and will not significantly affect the surgical duration or affect the care of the patient. The total impact on the surgical procedure, including placement of catheters and electromyogram sensors and stimulation testing, will not last longer than 30 minutes.

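### The experimental Selectivity Index is defined on peak urethral pressures with no stimulation-off reference, so read literally it mixes resting pressure with nerve recruitment

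*Protocol*

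**What the plan says.** Section 3.2.1 divides one branch's term by the sum of three: PPB (proximal urethra), DPB (distal urethra) and IRN (anal EMG). For the experimental index, "For experimental SI, PPB and DPB are the maximal intraurethral pressures measured at proximal and distal sphincter locations". The third term is described separately: "IRN is the maximum, normalized rectal nerve response". For the model index, "PPB, DPB, and IRN represent the percentage of model axons activated within the proximal perineal, distal perineal, and inferior rectal nerves, respectively".

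The index is meant to show "selective recruitment of any individual pudendal nerve branches (SI > 0.67, for example"), so 0.67 is an illustration. Adaptations are allowed: "The SI calculation may be modified in some patients, as necessary, for factors such as the presence of a short urethra". The other factor named is extra perineal EMG sensors; a baseline correction is not mentioned. The definition is carried to visit 4, where "experimental Selectivity Indexes will also be calculated as described above".

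Section 1.5 lists the SI, for patient and for simulated stimulation, among the secondary outcomes. For visit 2, section 2.4 says: "These catheters and electromyogram sensors will be recorded from continuously during the implant procedure". Section 3.2.3 compares leak point pressure with and without stimulation. Section 3.2.1 has no counterpart for the SI.

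**The concern.** A peak pressure is whatever was present before the pulse train plus whatever the train added. Only the second part reflects nerve recruitment. If the urethra has any pressure at rest, PPB and DPB are above zero with no axon activated, whereas the model terms would be zero.

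Two errors follow. A contact that truly recruits one branch gets an index diluted toward the resting ratio. A contact that recruits nothing gets an index equal to the resting ratio, which can look selective if one site has much the higher resting pressure. In either case the experimental and model indices can differ, or happen to agree, for reasons unrelated to the quality of the model.

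The protocol is alert to this kind of background elsewhere. Section 1.1 notes, for animal work, that anesthesia can affect urethral tone, and the primary bladder metric in section 3.2.2 is worded as an evoked contraction.

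**Working it through.** **Inputs from the protocol.** The SI formula, the definitions of its terms and the example cut-off of 0.67 (section 3.2.1). The cut-off has no derivation, so there is no stated figure to reproduce.

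**Assumptions.** The documents give no resting or evoked urethral pressures. All pressures below are illustrative, in cmH2O. Two urethral sites are measured, peak = rest + evoked rise, and IRN is 0 unless shown. Model terms are taken as zero without stimulation.

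**What the literal formula measures.** Let the resting pressures be R_P and R_D and the evoked rises E_P and E_D. With IRN = 0,

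SI_D = (R_D + E_D) / (R_P + R_D + E_P + E_D).

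This is a weighted average of the resting ratio R_D/(R_P + R_D) and the evoked ratio E_D/(E_P + E_D). The weight on the resting ratio is (R_P + R_D)/(R_P + R_D + E_P + E_D). Only the evoked ratio is of interest.

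**Missed selectivity.** Take equal rest R at both sites and a rise E at the distal site only. The evoked ratio is 1.0. As written, SI_D = (R + E)/(2R + E). To exceed 0.67:

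R + E > 0.67(2R + E), so 0.33E > 0.34R, so E > 1.03R.

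The rise needed is 10.3 at R = 10, 20.6 at R = 20, 41.2 at R = 40, 61.8 at R = 60 and 82.4 at R = 80.

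**False selectivity.** With no evoked rise, the index for the site with the higher rest is a/(a + b), where a and b are the two resting pressures. It exceeds 0.67 when a/b > 0.67/0.33 = 2.03.

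**Worked cases.**

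| Rest prox/dist | Evoked prox/dist | IRN | Index | As written | After subtraction |
|---|---|---|---|---|---|
| 30/30 | 0/20 | 0 | DPB | 50/80 = 0.625 | 20/20 = 1.00 |
| 60/60 | 0/20 | 0 | DPB | 80/140 = 0.571 | 20/20 = 1.00 |
| 80/80 | 0/20 | 0 | DPB | 100/180 = 0.556 | 20/20 = 1.00 |
| 50/50 | 0/30 | 0.5 | DPB | 80/130.5 = 0.613 | 30/30.5 = 0.984 |
| 60/20 | 0/0 | 0 | PPB | 60/80 = 0.75 | 0/0, no index |
| 60/20 | 5/5 | 0.5 | PPB | 65/90.5 = 0.718 | 5/10.5 = 0.476 |
| 20/20 | 0/40 | 0.5 | DPB | 60/80.5 = 0.745 | 40/40.5 = 0.988 |

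The first four rows miss a selective contact and the next two meet the cut-off falsely. In the last row the value changes but the classification does not, so the consequence depends on the pressures.

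**Subtraction alone is not enough.** If negative changes are simply set to zero, a distal drift of +1 with a proximal drift of -0.5 and IRN = 0 gives SI_D = 1/1 = 1.0 for an ineffective contact. A minimum response is needed as well.

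**The case against.** The strongest reply is that the protocol is silent rather than wrong. It nowhere says that the pressures are uncorrected. The index is calculated for a stimulation electrode location, and the rectal term is called a response. Baseline windows are the kind of signal processing that a statistical analysis plan may hold, and that document is not shown. A reader might infer that the trial will in fact compute the index on unsubtracted pressures. The documents do not establish that, because nothing forbids subtraction. What remains is that the protocol does more than leave a gap: it writes out the formula and says what each term is. The modification clause covers some patients, whereas a baseline is needed in all of them.

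Several limits on size also stand:

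- Every pressure above is assumed. The false-positive case needs more than a twofold difference in resting pressure between sites, and the documents do not show that this occurs.
- Section 5 expects 80% of participants to be women, and section 3.2.1 allows a modified SI where a short urethra permits only one pressure measure. The two-site expressions do not describe those participants.
- A reader might treat 0.67 as a decision rule. It is only an example, and no test, success criterion or treatment decision is tied to it. The pull toward the resting ratio does, however, affect the SI as a continuous measure at any cut-off.
- A reader might infer that model validation or the primary outcome is undermined. Section 2.6 says that voltage-field estimates will be checked against stage-1 recordings but does not name the SI. No participant-level agreement analysis between the two indices is specified. The primary outcome does not use the SI.

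**Conclusion.** The point holds as a defect in a stated definition. Followed literally, section 3.2.1 gives an experimental SI that blends resting pressure with recruitment and is not on the same footing as the model SI. The algebra needs only a non-zero resting urethral pressure. Under the two-site, zero-IRN assumptions, the thresholds are an evoked rise of about 1.03 times an equal resting pressure (missed selectivity) and a resting ratio of about 2.03 (false selectivity). How often either would occur in this trial cannot be determined from the documents.

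Confidence is moderate, because the analysts may intend a correction that the text does not state. The effect is confined to a secondary outcome. It should be corrected, but it does not threaten the primary result.

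The mismatch between raw pressures and a normalized IRN is a separate issue that subtraction does not cure. With evoked rises of 5 and 5 and IRN = 1, SI_IRN is still only 1/11 = 0.09.

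**What to change.** In section 3.2.1:

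- Define each experimental term as the stimulation-evoked change: the peak during the train minus the mean over a fixed window just before that train, from the same sensor at the same visit.
- Pre-specify a minimum response, for example a multiple of that sensor's pre-train variability. Count any smaller change as zero.
- Report no SI when no sensor reaches the minimum, and count such trains separately.
- Apply the rule to whichever sensors are used at each visit. Visit 2 uses anal EMG needles and visit 4 uses surface electrodes, so baselines should not be carried from one visit to the other.
- State that a short pre-train baseline is recorded at visit 4, since section 2.7 does not say that recording there is continuous.

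The cost is a few sentences of protocol text and a small change to the analysis code. At visit 2 the continuous recording already allows the correction at analysis, so no visit 2 data need be lost. At visit 4 the addition is a brief recording before each train. The scaling of IRN against the pressures should be settled separately.

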1.5 Secondary Outcomes

The secondary outcome measures in this study will be 1) selectivity indices for selective stimulation of pudendal nerve branches for both patient stimulation and simulated model stimulation and 2) selectivity index for selective stimulation of pudendal nerve branches for simulated model stimulation. The SI calculation may be modified in some patients, as necessary, for factors such as the presence of a short urethra that only allows for a single intraurethral pressure measure (female urethras < male urethras) and/or the placement of EMG in the perineal floor between yields one or more additional sensors. 3) Measurement of effect of pudendal nerve stimulation on urethral leak point pressure (ULPP) using stimulation targeted for the external urethral sphincter.

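### The experimental Selectivity Index adds intraurethral pressures to a normalized anal EMG response, so its values and any selectivity cut-off depend on the arbitrary scale given to the EMG term

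*Protocol*

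**What the plan says.** Protocol section 3.2.1 gives one formula, SI_X = X / (PPB + DPB + IRN), and two sets of inputs for it.

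- **Model SI.** Each term is the "percentage of model axons activated within the proximal perineal, distal perineal, and inferior rectal nerves". All three terms are percentages.
- **Experimental SI.** "PPB and DPB are the maximal intraurethral pressures measured at proximal and distal sphincter locations. IRN is the maximum, normalized rectal nerve response". The same section takes IRN from the anal EMG sensor. It does not say what IRN is normalized to or what range it then has.

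The purpose is stated: "This SI will be used to determine whether any stimulation electrode combinations have selective recruitment of any individual pudendal nerve branches". A value of 0.67 is offered as an example of a cut-off.

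The section allows changes to the formula: "The SI calculation may be modified in some patients, as necessary, for factors such as the presence of a short urethra", or where a perineal EMG adds sensors. These changes concern the number of terms, not their scale. The definition is used again later: "During visit 4 experimental cystometrogram testing, experimental Selectivity Indexes will also be calculated as described above".

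Section 1.5 makes the index a secondary outcome: "selectivity indices for selective stimulation of pudendal nerve branches for both patient stimulation and simulated model stimulation".

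**The concern.** A share of a total has meaning only if the parts are measured on one scale. The model SI meets this condition. The experimental SI, as defined, does not: two terms are pressures and the third is a unitless EMG response. Whatever range is chosen for IRN acts as an exchange rate between pressure and EMG, and nothing in the protocol justifies one rate over another. Changing the pressure unit would have the same effect.

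At stake is the one use that section 3.2.1 gives to the index. The same recording could be reported as selective for a urethral branch, for the anal branch, or for none, according to a scaling choice that has nothing to do with the nerve. The direction of the error cannot be stated in advance, because it reverses with the IRN scale.

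**Working it through.** **Inputs.** The formula, the nature of each term and the example cut-off of 0.67 come from section 3.2.1. That section gives no pressures, no EMG values and no IRN range, so those below are assumptions. I use cmH2O because it is the only pressure unit in the protocol (sections 1.4, 3.2 and 3.2.2). The protocol does not derive 0.67 from anything, so there is no figure of its own to reproduce.

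**Algebra.** Let P and D be the two pressures, I the anal response as a fraction of its maximum, and c the full-scale value given to IRN, so that IRN = cI.

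- SI_PPB = P / (P + D + cI)
- SI_DPB = D / (P + D + cI)
- SI_IRN = cI / (P + D + cI)

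Each value changes with c. The ratio SI_PPB : SI_DPB = P : D does not.

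**Example 1.** P = 30, D = 5, I = 0.8.

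- IRN on 0-1 (c = 1): the sum is 30 + 5 + 0.8 = 35.8. SI_PPB = 30/35.8 = 0.84 and SI_IRN = 0.8/35.8 = 0.02.
- IRN on 0-100 (c = 100): the sum is 30 + 5 + 80 = 115. SI_PPB = 30/115 = 0.26 and SI_IRN = 80/115 = 0.70.

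Against 0.67, the recording is selective for the proximal perineal branch on the first scale and for the anal branch on the second.

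**Example 2.** P = 20, D = 5, I = 1.

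| Full scale c | SI_PPB | SI_DPB | SI_IRN | Above 0.67 |
|---|---|---|---|---|
| 1 | 20/26 = 0.769 | 5/26 = 0.192 | 1/26 = 0.038 | PPB |
| 10 | 20/35 = 0.571 | 5/35 = 0.143 | 10/35 = 0.286 | none |
| 100 | 20/125 = 0.160 | 5/125 = 0.040 | 100/125 = 0.800 | IRN |

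**What a full anal response needs in order to pass 0.67.** SI_IRN > 0.67 requires P + D < IRN × 0.33/0.67. That is 0.49 cmH2O if IRN runs 0-1, and 49.3 cmH2O if it runs 0-100. On the first scale anal selectivity is practically out of reach; on the second it is easily met.

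**Two-term form (one urethral pressure plus IRN).** Values here also depend on c. With 20 cmH2O and a full anal response, SI_PPB is 20/21 = 0.95 for c = 1 and 20/120 = 0.17 for c = 100.

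**Check of the repair.** In example 1, divide each term by a reference for its own channel, assumed to be 30 cmH2O, 20 cmH2O and a full anal response. The terms become 1, 0.25 and 0.8, with sum 2.05. SI_PPB = 1/2.05 = 0.488 and SI_IRN = 0.8/2.05 = 0.390. In percent, 100/205 gives the same 0.488, so the choice of scale no longer matters. The choice of reference still does: with a DPB reference of 30 the terms are 1, 0.167 and 0.8, and SI_PPB becomes 1/1.967 = 0.508.

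**The case against.** The strongest reply is that the text is brief, not wrong. Channel-level signal processing is often settled in an analysis plan, which is not shown here, and the team may normalize the pressures in practice. This stands in part: the protocol's wording does not prove that the final calculation will mix scales. But the wording does define the experimental PPB and DPB as pressures. A later document that only stated the IRN range would leave the mixture in place; one that cured it would have to redefine those two terms.

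It is also fair that 0.67 is only an example, that no test or success rule rests on the index, and that every magnitude above uses assumed inputs and contrasts two widely separated IRN scales. The figures show how sensitive the index can be, not how large the error will be. Any fixed cut-off has the same dependence, however.

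Two stronger readings are tempting.

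- **That rankings of stimulation settings are invalid.** A ranking by SI_PPB can reverse. Compare the setting in example 1 with another at 30 and 20 cmH2O and a 20% anal response. The second setting gives 30/50.2 = 0.60 against 0.84 on 0-1, but 30/70 = 0.43 against 0.26 on 0-100. Yet no section says that settings will be ranked by SI. Ranking by SI_IRN, and ranking in a two-term index, would not change with the scale in any case.
- **That a planned numerical comparison of patient and model SI fails.** Section 1.5 lists the two together but states no such comparison. If they are set side by side, the mixed scale would distort the reading; the protocol does not go further than that.

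**Conclusion.** The point holds for the definition as written. Section 3.2.1 fixes a sum of unlike quantities for the experimental SI, and no other section puts them on one scale. The absolute values, and any cut-off used to declare a branch selectively recruited, therefore rest on the IRN scale. Under the assumed 30 and 5 cmH2O with an 80% anal response, SI_PPB moves from 0.84 to 0.26 and SI_IRN from 0.02 to 0.70 between a 0-1 and a 0-100 scale.

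The reach is limited to a secondary outcome (section 1.5) and its repeat at visit 4. A reader might infer that the primary outcome or the number of participants is undermined. They are not: the primary outcome is a bladder-pressure criterion, and the sample size in section 3.1 does not use the SI. The flaw should be corrected, since the index cannot serve its stated purpose without a common scale.

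**What to change.** In section 3.2.1, define the three experimental terms alike: each is the stimulation-evoked response of its channel, expressed as a fraction of a stated reference for that same channel. Name the reference; the largest response of that channel in the same participant and session is one option. When the number of sensors is modified, compute the model SI on the same channels.

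The cost is low: revised wording and re-scaling of signals already recorded, with no added visit or measurement.

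The drawback should be stated in the text. Own-channel scaling scales up a weakly recruited channel, and with a session maximum as reference the SI depends on which settings were tested. In the check above, raising the DPB reference from 20 to 30 moved SI_PPB from 0.488 to 0.508. For the comparison setting at 30 and 20 cmH2O with a 20% anal response, it moves from 1/2.2 = 0.455 to 1/1.867 = 0.536, which reverses the order of the two. Common scaling removes the arbitrary exchange rate; it does not make values or rankings independent of the test set, and they should be read with that limit.

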Sacral neuromodulation (SNM) is a standard clinical treatment. FDA approval was granted for the Medtronic Interstim implantable neurostimulator over 20 years ago [4], and over 200,000 people worldwide have been implanted. The Interstim system consists of an implantable pulse generator (IPG) and a stimulation lead. The lead consists of helical-coiled, insulated wires that terminate in four ring electrodes near the tip. The Interstim lead has barbs, or tines, along the distal end to provide anchoring and limit migration. For an initial evaluation phase (“stage 1 implant”), the stimulation lead is placed through the third sacral foramen, generally using fluoroscopy, and externalized percutaneously to a stimulator worn on the waist [24]. During implant, anal bellows and/or patient sensations are typically used to determine relative nerve activation for different stimulation amplitudes and electrode combinations. If the patient has had sufficient improvement in symptoms (generally > 50%) after a 2- or 3-week observation period, the IPG is implanted in the lower back and connected to the stimulation lead, leaving a fully-implanted system (“stage 2 implant”). Externally, a programmer can communicate with the IPG to monitor or modulate stimulation. Stimulation can be delivered bipolar between any pair of the four electrodes or monopolar between one electrode and the IPG.

Since 2005, a few clinicians worldwide have started placing the Interstim lead at the pudendal nerve [21], [25], [26]. This is often done in patients who failed traditional SNM or who have concurrent pelvic symptoms [27]. The clinical steps for this pudendal nerve implant procedure follows the steps for SNM, in an off-label use, with fluoroscopy and external anal sphincter (EAS) electromyogram (EMG) used to determine the proximity of the lead to the pudendal nerve [28], [29]. Patients at the University of Michigan health system who receive the Interstim at the pudendal nerve offer an opportunity to develop a new computational model of pudendal nerve electrical stimulation. Development of this model and validation of our ability to model the nerve and stimulation lead will suggest whether it is possible to selectively stimulate the nerve such as to drive bladder excitation and voiding. Thus the goal of this study is to gather imaging data about the location of the nerve and stimulation lead, to create a computational model of the

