2.6 Patient-specific computational model (involves no direct patient interaction) (Aim 3)

As part of the research study, the pudendal nerve for each patient will be identified and segmented from the MRN images with Materialise Mimics Innovation Suite (Figure 2). We will co-register the three-dimensional surfaces from MRN, DTI, and CT images to create a patient-specific computational model, as has been done for other types of implantable neurostimulators [30], [52]. A software program (Comsol Multiphysics) will be used to estimate voltage fields generated by the neurostimulator electrode stimulation. These estimates will be validated using stage-1 recordings. The computational model will be used to predict electrode stimulation parameters for recruiting different parts of the pudendal nerve using the NEURON computational software. Computational modeling of implanted stimulator activation of nerves has been done previously by our research team [53]. The computational model produced with the Mimics Innovation Suite will not be used to diagnose or be used as a diagnostic procedure. These software programs will be used to determine our ability to model the nerve and electrode.

[figure not shown]

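### The model-based Selectivity Index has no minimum response, so its any-combination, any-branch rule can label near-zero recruitment as selective

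*Protocol*

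**What the plan says.** Section 1.5 of the Protocol makes selectivity indices secondary outcomes, for patient stimulation and for the simulated model. Section 3.2.1 gives the formula: SI for branch X is X/(PPB + DPB + IRN), where the three terms are the responses of the proximal perineal, distal perineal and inferior rectal branches.

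The terms differ between the two versions of the index:

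- Model-based: "PPB, DPB, and IRN represent the percentage of model axons activated within the proximal perineal, distal perineal, and inferior rectal nerves, respectively".
- Experimental: "For experimental SI, PPB and DPB are the maximal intraurethral pressures measured at proximal and distal sphincter locations", and "IRN is the maximum, normalized rectal nerve response".

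The same section then fixes what the index is for, which is to determine "whether any stimulation electrode combinations have selective recruitment of any individual pudendal nerve branches (SI > 0.67, for example"). It allows changes to the calculation: "The SI calculation may be modified in some patients, as necessary, for factors such as the presence of a short urethra". The other example it gives is extra EMG sensors in the perineal floor. Both examples concern which sensors are available, not how large a response must be.

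No minimum response for the SI appears in 3.2.1, in the secondary outcomes (1.5) or in the visit descriptions (2.4, 2.7). The 20 cmH2O threshold in 1.4, 3.2 and 3.2.2 applies to bladder contraction and not to the SI.

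**The concern.** A ratio of responses measures how recruitment is shared among the branches. It says nothing about how much recruitment there is. That is harmless when every setting evaluated gives a substantial response, but the protocol does not require this. Section 2.4 varies amplitude and pulse width through each contact, so weak settings are to be expected, and a model can be run at any amplitude.

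The decision rule makes this worse, because it asks whether any combination is selective for any branch. The answer is then set by the most extreme ratio found, and the most extreme ratios occur where only one branch has just begun to respond.

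At stake is the meaning of a positive finding. Section 1.1 says the modelling should suggest whether the nerve can be stimulated selectively so as to drive bladder excitation and voiding. Activating a trace of one branch does not answer that. Section 3.2 also plans to relate the ability to model and stimulate the nerve selectively to participant characteristics. If that ability were summarised by the yes/no classification, nearly all participants could fall in one class.

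**Working it through.** **Inputs.** The formula, the definition of the model terms and the example cut-off of 0.67 come from Protocol 3.2.1. The protocol gives no worked SI value and no derivation of 0.67, so there is no figure to reproduce. The recruitment percentages below are illustrative assumptions.

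**1. The index ignores size.** Multiplying all three terms by the same factor leaves the SI unchanged:

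- 1% / 0.25% / 0.25%: 1/(1 + 0.25 + 0.25) = 0.667
- 90% / 22.5% / 22.5%: 90/(90 + 22.5 + 22.5) = 0.667

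Target recruitment differs ninety-fold and the score is the same.

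**2. What the cut-off requires.** SI > c holds when the two off-target percentages total less than X(1/c − 1). For c = 0.67 the factor is 1/0.67 − 1 = 0.4925:

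- X = 1%: passes if off-target recruitment totals less than 0.49 percentage points.
- X = 90%: passes if it totals less than 90 × 0.4925 = 44.3 percentage points.

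**3. The two edge cases.**

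- 1% / 0% / 0%: 1/1 = 1.00, the highest possible score.
- 0% / 0% / 0%: 0/0, undefined.

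**4. Can another cut-off cure it?** No. A score of 1.00 exceeds every c below 1.00, so the 1% / 0% / 0% setting passes whatever value replaces the example of 0.67.

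**5. What the decision rule then does.** As amplitude rises for a given electrode combination, one branch will usually reach threshold before the other two. Between its threshold and the next one, that branch has some active axons and the others have none, so its SI is exactly 1.00. One such setting is enough for the rule to answer yes.

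**6. Effect of a floor.** With an assumed minimum target recruitment of 5%, 10%, 20% or 50%, the 1% / 0% / 0% setting no longer counts as selective at any of the four. A setting of 90% / 20% / 20% keeps its score of 90/130 = 0.692 and still counts at all four.

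**7. Does this carry over to the experimental SI?** Not automatically. The urethral terms are maximal pressures with no stated baseline subtraction, and the reference for normalising the rectal term is not given. With assumed values:

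- Pressures of 40 and 40 cmH2O, rectal response 1 on a 0–1 scale: shares 0.494 / 0.494 / 0.012.
- The same pressures, rectal response 100 on a 0–100 scale: shares 0.222 / 0.222 / 0.556.

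Neither passes 0.67. If resting pressure stays in the terms, a weak response does not push the index to 1.00.

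**The case against.** The strongest reply is that a detection floor, the handling of 0/0 and the reporting of recruitment beside the index are details for an analysis plan, which may exist unseen. In addition, 0.67 is only an example, no hypothesis test is tied to it, and this is a mapping study. The status of the cut-off and of the outcome is fairly put and limits the weight of the point. But the protocol does not leave the matter open: it fixes the formula and the decision made from it, and step 4 shows that choosing another cut-off would not help.

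Four stronger readings are tempting, and the documents do not support them.

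- **That the index wrongly rejects strong settings.** A setting of 90% / 30% / 15% scores 90/135 = 0.667 and misses 0.67. It also recruits 45 percentage points off target. Rejecting it is what a selectivity ratio is for, and a floor would not change the result.
- **That a false-positive rate for the experimental SI can be simulated from noise.** That needs resting pressure removed, all three terms on a common scale, an SI for each setting and independent settings. Section 3.2.1 states none of these. It introduces the index per electrode location, so the maxima may run across amplitudes, and a near-threshold setting would then have no SI of its own.
- **That ten configurations are searched at visit 2.** Section 1.1 says "Stimulation can be delivered bipolar between any pair of the four electrodes or monopolar between one electrode and the IPG", which would make 4 monopolar and 6 paired configurations. That is background on the device, and its monopolar mode uses a pulse generator that is not implanted until stage 2.
- **That the index steers visit 4 towards weak settings and so harms the 20 cmH2O outcome.** Section 2.6 says the model will "predict electrode stimulation parameters for recruiting different parts of the pudendal nerve", and 2.7 applies paradigms identified by the model. Neither says that they are ranked by SI, and 2.7 lets contacts, pulse width, frequency and amplitude be varied on the day.

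**Conclusion.** The point holds for the model-based SI. As written, the rule can call a setting selective on 1% recruitment of one branch, leaves the SI undefined when nothing is activated, and can hardly return a negative answer wherever one branch reaches threshold first. A positive result would therefore not show useful selective recruitment.

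This rests on two assumptions: that the model SI is evaluated at individual settings, including some just above the lowest threshold, and that the three branches do not reach threshold together. The protocol rules out neither. If the model were evaluated only at amplitudes that give substantial recruitment, the problem would be small.

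For the experimental SI the point is conditional. It applies if baseline is removed and the index is computed per setting, and the protocol does not say whether either is so. No error rate can be attached to it. The primary outcome does not use the SI and is not affected.

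**What to change.** In 3.2.1:

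1. Compute the SI only where at least one branch exceeds a response floor set in advance. For the model, this is a minimum percentage of axons activated. For patients, it is a response above the stimulation-off mean plus a set multiple of its standard deviation.
2. Call a setting selective only if the SI exceeds the cut-off and the target branch itself reaches a recruitment level set in advance.
3. Report target-branch recruitment beside each SI, with the number of settings tested and the number below the floor.

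The documents give no basis for particular values of the floor or the recruitment level, so the investigators should choose and justify them before the indices are examined. Section 2.4 has the sensors recorded continuously during the implant procedure, so stimulation-off stretches should be available there.

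The cost is one paragraph and a filter in the analysis code; no visit or procedure changes. The downside is that some near-threshold settings drop out and fewer settings will be called selective.
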